	Safety follow-up will be performed at 28 and 60 days after				
	discharge. For the Early Termination (ET) of treatment, participants should follow the routine from visit 17: End of Treatment (D15), in advance. The study will be considered completed when the last				
	participant completes his or her last visit.				
	Individuals with the following characteristics will be				
	included in this study:				
	Age ≥18 years, regardless of gender;				
	2. Patients hospitalized in moderate to severe stages in				
	line with the Ministry of Health classification ¹ ;				
	3. Positive diagnostic test for SARS-CoV-2 by molecular				
INCLUSION CRITERIA	amplification of the virus in RT-PCR diagnosed from				
	respiratory specimen (nasopharyngeal, oropharyngeal,				
	lower respiratory tract [e.g., sputum]) collected <96				
	hours before randomization;				
	4. Time between symptom onset and inclusion ≤14 days;				
	5. Hospitalization within 48 hours of study inclusion;				
	6. Availability for follow-up during the study period;				

Mild: Flu-like syndrome (cough, sore throat or runny nose), followed or not by: Anosmia (olfactory dysfunction) Ageusia (gustatory dysfunction), Runny nose, Diarrhea, Abdominal pain, Fever, Chills, Myalgia, Fatigue, Headache;

Moderate: Persistent cough + daily persistent fever or Persistent cough + progressive worsening of another symptom related to COVID-19 (adynamia, prostration, hyporexia, diarrhea) or at least one of the above symptoms + presence of a risk factor.

Severe: Severe acute respiratory syndrome - influenza syndrome presenting: Dyspnea/respiratory distress or persistent chest pressure or $_{02}$ saturation less than 95% on room air or bluish coloration of lips or face.

 $^{^{\}mathrm{1}}$ The Brazilian Ministry of Health classifies the symptoms of COVID-19 into:

	7. Voluntary adherence to participate in the study and				
	signing the Informed Consent Form.				
	Individuals with one or more of the following characteristics				
	will not be eligible to participate in this study:				
	1. Patients known or suspected to be sensitive to				
	AZVUDINE or excipients (inactive ingredients:				
	microcrystalline cellulose, hydrated lactose,				
	polyvinylpyrrolidone K30, croscarmellose sodium,				
	magnesium stearate);				
	2. Patients diagnosed with pneumonia caused by other				
	pathogens;				
	3. Patients with liver disease (total bilirubin ≥2mg/dL,				
	ALT/TGP and AST/TGO ≥5 times above normal limit); ²				

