	4) Loss of contact with the participant for follow-up;			
	5) Death;			
	6) Hospital discharge (2 negative RT-PCR tests).			
	The following criteria define the interruption of thestudy			
	as a whole:			
	1) Termination of the trial by the sponsor, if justified;			
	2) Termination of the study by the Principal			
	Investigator, if justified;			
	3) Termination of the study at the request of local			
	ethical and health authorities.			
	Demographic data collection, physical examination, vital			
	signs assessment, blood sampling, respiratory tract			
PROCEDURES	sampling, imaging, ECG, and pregnancy testing (female			
	participants) will be performed			
OUTCOME/ENDPOINTS	PRIMARY ENDPOINT			

- Proportion of participants with clinical status improvement [Period: until D15, approximately 14 days].
 - The criterion for a participant to have an improvement in clinical status is a decrease on the WHO Clinical Improvement Ordinal Scale in at least one category compared to screening (WHO, Jun/2020).

SECONDARY ENDPOINT

- Proportion of participants with a clinical outcome of cure during the study; [Period: until D15, D21, and D28, approximately 14-30 days].
 - The clinical endpoint of cure is defined in this protocol as the absence of viral RNA in collected samples and clinical conditions for hospital discharge³.
- Time to normalization of body temperature (below 37.6°C axillary); [Period: until D15, D21 and D28, approximately 14-30 days]
- Time to improvement of diarrhea, myalgia, fatigue, malaise, cough, dyspnea, and headache; [Period: until D15, D21, and D28, approximately 14-30 days].

³ According to the WHO Working Group on Characterization and Clinical Management of COVID-19 Infection (July, 2020), clinical and virological absence of infection (non-detectable RT-PCR) is suggestive of CURE for initially infected participants.

- Changes in liver and kidney function baselines, and inflammatory and immunological markers: [Period: until D15, D21 and D28, approximately 14-30 days]
 - Lab tests performed on days D1, D3, D5, D7,
 D9, D13, D15, D21, D28, and D60.
- Evaluation of the time to negative conversion of the SARS-CoV-2 viral load by RT-PCR between AZVUDINE (FNC) group and control group; [Period: until D15, D21 and D28, approximately 14-30 days].

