- Symptom monitoring, vital signs, oxygen and blood glucose measurement;
- Collection of blood samples and respiratory sample (nasal and oropharyngeal
- swab) for safety and efficacy monitoring tests;
- CT scan of the lung and electrocardiogram.
- Collecting blood for a pregnancy test (women of childbearing age).

VISIT 18: FOLLOW-UP (D21)

Participants who, even after the end of treatment, remain in the hospital must undergo the procedures and tests for safety and efficacy monitoring that are scheduled to occur approximately 7 days after the administration of the last dose of the investigational drug or PLACEBO.

The following procedures will be performed at the V18 visit:

- Monitoring drug interactions and AEs;
- Symptom monitoring, vital signs, oxygen and blood glucose measurement;
- Collection of blood samples and respiratory sample (nasal and oropharyngeal
- swab) for safety and efficacy monitoring tests;
- CT scan of the lung and electrocardiogram;

Participants who are not discharged from the hospital after the end of treatment will be required to follow the follow-up schedule on D28 and D60. However, safety procedures and examinations will not be exclusive to these days and research participants who still remain hospitalized will be assisted at all times by the Principal

Investigator and his team.

VISIT 19: FOLLOW-UP (D28)

Two weeks after discharge from the hospital, the volunteers will return to the research center for procedures and tests to monitor safety and efficacy after the end of treatment.

The following procedures will be performed at the V19 visit:

- Symptom monitoring, vital signs, oxygen and blood glucose measurement;
- CT scan of the lung and electrocardiogram.

The Principal Investigator may adjust the procedures performed during the hospital visit according to the condition of the research participant and the results of the clinical examinations.

VISIT 20: FOLLOW-UP (D60)

60 days after discharge from the hospital, the volunteers will return to the research center to undergo procedures and tests to monitor safety and efficacy.

The following procedures will be performed in visit V20:

- Symptom monitoring, vital signs, oxygen and blood glucose measurement.
- Collecting blood for a pregnancy test (women of childbearing age).

The Principal Investigator may order tests according to the participants' previous results.

IGZ-1

AZVUDINE Clinical Trial Design

Schedule of visits and procedures

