Week/Day	D-1	D0	D1	D2	D3	D4	D5	D6	D7	D8	D9	D10	D11	D12	D13	D14	D15 after the start of treatment	D21 ⁵ after the start of treatment	D28 after start of treatment	D60 after the start of treatment ³
Visit	1	2	3	4	5	6	7	8	9	10	11	12	13	14	15	16	17	18	19	20
Interval of the visit	± 4 days	-	-	-	-	-	-	-	-	-	-	1	1	1	-	-	Antes da alta hospitalar	± 3 dias	± 3 dias	± 3 dias
STAGES	TREAT	RANDOMIZATION							BLINDI	ED TRE	ATMEN	NT¹					END OF TREATMENT ²		FOLLOW-UP	
TCLE	Х																			
DEMOGRAPHIC INFORMATION	Х																			
ANAMNESIS	Х																			
ELIGIBILITY CRITERIA	Х																			
RANDOMIZATION		X																		
DISPENSING OF THE MEDICATION		Х																		
MEDICATION ACCOUNTING		X																		
SYMPTOM MONITORING	Х					•	•			Χ		•	•	•	•	•	X	X	Х	X
VITAL SIGNS	Х		X									Χ	Χ	X	X					
FINGER OXYGEN PULSE	Х		X									Х	X	Х	Х					
BLOOD GLUCOSE			X										Х	X	Х	Х				
PREGNANCY EXAM ⁴	Х																X			X

IGZ-1

AZVUDINE Clinical Trial Design

CT LUNG		Х		Χ				Χ				Χ				X	X	X	
ECG		Χ										Χ				Χ	X	X	
RT-PCR	Х	Х		Χ		Χ		Χ		Χ		Χ		Χ		Χ	X	X	
BIOCHEMICAL EXAMINATIONS	Х	Х		Χ		Χ		Х		Χ		Χ		Х		Χ	X	Х	
T-LYMPHOCYTES		Χ		Χ		Χ		Χ		Χ		Χ		Χ		Χ	X	X	
СВС		Χ		Χ		Χ		Χ		Χ		Χ		Χ		Χ	X	X	
FUNCTION OF COAGULATION		Х														Χ	X	X	
ESR/VHS		Χ						Χ								Χ	X	X	
CARDIAC MARKERS AND ENZYMES		Х						Х								X	Х	Х	
C-REACTIVE PROTEIN		Χ						Χ								Χ	X	X	
PROCALCITONIN		Х						Х								Χ	X	Х	
IL-6		Χ						Χ								Χ	X	X	
PHOSPHORUS IN URINE		Χ														Χ	X	X	
IMMUNOLOGICAL MARKERS		Х															Х	Х	
INFECTIOUS DISEASES		Χ																	
RESPIRATORY PARASITES		Х																	
TRIPLE TEST FOR RESPIRATORY PARASITES		Х															Х	Х	
AZVUDINE OR PLACEBO ADMINISTRATION			X																

IGZ-1

AZVUDINE Clinical Trial Design

MONITORING DRUG INTERACTIONS		X	X		
AE MONITORING		X	X		

Tabela 10: Cronograma de visitas e procedimentos do estudo.

¹ Day 1 of administration will be recorded as day 1 (D1) and the treatment days follow until day 14 (D14). The Principal Investigator may adjust the procedures performed during treatment according to the condition of the research participant and the results of clinical examinations (the condition manifests itself more rapidly in some patients and these patients should be observed closely).

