² The examinations and procedures under visit 17 (D15) must be performed by all participants as soon as the treatment is terminated, including participants who have stopped treatment early (AT) and for any other reason.

³ The. procedures and examinations planned to be performed at visit D28 and D60 will be determined by the Principal Investigator according to the participants' previous examinations.

⁴ For women of childbearing age only.

⁵ Visit 18 procedures will be performed only on research participants who are still hospitalized.

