8.7. AE COLLECTION AND REGISTRATION

Any information relevant to the trial should be recorded from the first administration to the end of follow-up. AEs will be monitored throughout the study and the Principal Investigator, or someone deligated by him, will be responsible for recording all adverse medical events observed during the study, in detail, in the source documents and in each participant's eCRF, during the study period from the first dose to the end of follow-up, regardless of severity and causal relationship to the study drug.

All SAEs must also be recorded in eCRF as soon as they occur, and the information provided in the SAE report form must be consistent with the event-related data that is recorded in eCRF. All AEs, SAEs and special interest AEs must include the following content in detail:

• **Description:** Events should be described in medical terms, rather than the words used to record the participants' reports in the original document. If

applicable, symptoms, signs, laboratory abnormalities, and diagnosis should be included. If the same AE occurs more than once, in the same participant, and the participant recovered from both events, the AE should be recorded twice.

- Date of occurrence: the date when the AE first occurred in the participant or
 the date when the symptoms related to the AE occurred should be recorded. If
 the AE is the test result of an abnormal laboratory test or test with clinical
 significance, the date of occurrence is the date the test was performed.
- Date of result: the date of resolution of the AE-related symptoms should be recorded.
- AE intensity and severity: classified as: (1) mild, 2 (moderate), 3 (severe) or 4 (complete/severe impairment). ¹⁶
- Causal relationship between AE and study drugs: as per Table 5.
- Measures for the study drug: It should be recorded whether the participant
 continued using the drug or had to stop using it as a result of the AE or SAE. If
 the reaction occurred after the end of treatment, this item does not apply.
- Measures for AE: It should be recorded what measures were taken to solve the
 AE, such as drug therapy and/or non-drug therapy, hospitalization, surgery,
 among others. If no action was taken, this fact should be reported.
- **Outcome:** the disappearance of signs or symptoms; recovery with sequelae; stability; worsening; death; or loss to follow-up must be recorded.

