9.1. CONCLUSION OF THE PARTICIPANT

At the end of the treatment period of up to 14 days or when the coronavirus viral load detection by RT-PCR is negative on two consecutive occasions, considering a difference of at least 24 hours between the two sample collections, the study medication

will be discontinued and the participant continues with the standard treatment therapy. Treatment may also be discontinued if the Principal Investigator deems it best for the participant's safety, or if the participant decides not to continue with treatment. In either situation, follow-up will be done on days D28 and D60 after the end of treatment.

The participant will only be discharged from the hospital at the end of treatment after medical evaluation by the Principal Investigator. The participant will be required to return to the hospital for follow-up visits. After the last visit, the subject's participation in the study will be considered terminated.

The need for additional intervention or the occurrence of safety endpoints/endpoints do not constitute trial completion and are not criteria for withdrawal from the trial or the trial medication.

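### Follow-up visits have conflicting time origins, so D28 data may be collected on a study day that depends on when the participant goes home

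*Protocol*

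**What the plan says.** The protocol dates the D28 visit in several ways.

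- Table 10 heads the column "D28 after start of treatment", with an interval of ±3 days. Section 7.5 repeats the three-day tolerance for D28 and D60.
- Section 7 (opening text) puts D28 at two weeks, and D60 at sixty days, from end of treatment.
- Section 9.1: "follow-up will be done on days D28 and D60 after the end of treatment".
- Section 7.3, Visit 19: "Two weeks after discharge from the hospital, the volunteers will return to the research center". Visit 20 is placed 60 days from discharge.
- Synopsis: "Safety follow-up will be performed at 28 and 60 days after" discharge. Section 5.1.1 also counts 28 and 60 days from discharge.

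D21 is counted from start of treatment in Table 10, but section 7.3 places it "approximately 7 days after the administration of the last dose of the investigational drug or PLACEBO". Table 10, footnote 5, limits it: "Visit 18 procedures will be performed only on research participants who are still hospitalized".

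The synopsis list of events that end the study for a participant includes, as item 6, "Hospital discharge (2 negative RT-PCR tests". Section 9.3 has no such item, and section 9.1 ends participation after the last visit.

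For adverse events, section 8.7 requires recording "during the study period from the first dose to the end of follow-up". The visit lists in section 7.3 name AE monitoring for Visits 3 to 18, and not for Visit 19 (D28) or Visit 20 (D60). Most secondary endpoints, including laboratory markers, viral load, imaging, AEs and mortality, carry the periods D15, D21 and D28 (section 4).

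**The concern.** A comparison at D28 needs the same elapsed time from a common origin in both arms. Discharge is not a common origin. It happens after randomisation, and two negative RT-PCR tests, the effect the drug is expected to hasten, are one of its criteria. If sites schedule by section 7.3, an arm that goes home sooner has its D28 symptoms, CT, laboratory tests and RT-PCR taken earlier in the illness. A difference in those values would then mix the treatment effect with a difference in timing.

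Three further points concern who is observed, and for how long. A site that follows synopsis item 6 would close out participants at discharge and lose their later visits. D21 laboratory and viral-load values exist only for people who have not gone home, a group selected by outcome. A discharged participant skips Visit 18, so the last AE check listed in 7.3 is Visit 17, about 24 hours after the last dose.

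Safety is part of the primary objective. Section 11.3 analyses SAE occurrence by logistic regression on allocation group, and AEs by t, Mann-Whitney or chi-square tests. None of these allows for unequal observation time.

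**Working it through.** The plan has no calculated figure on this point, so the check is calendar arithmetic.

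**Inputs.** Let d be the study day of discharge and e the day treatment ends, with D1 the first dose. I assume that treatment runs until discharge or day 14, so e = min(d, 14). Section 6.2.4 stops the drug when hospital care ends. Someone who stops earlier and stays in hospital would have a smaller e.

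**Study day of the D28 visit under each rule:**

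| d | Table 10: 28 | Section 7.3: d + 14 | Synopsis, 5.1.1: d + 28 | Section 7: e + 14 | Section 9.1, read literally: e + 28 |
|---|---|---|---|---|---|
| 5 | 28 | 19 | 33 | 19 | 33 |
| 7 | 28 | 21 | 35 | 21 | 35 |
| 11 | 28 | 25 | 39 | 25 | 39 |
| 14 | 28 | 28 | 42 | 28 | 42 |
| 21 | 28 | 35 | 49 | 28 | 42 |

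**Agreement with Table 10.** Its window is 28 ± 3, that is days 25 to 31.

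- Section 7.3: 25 ≤ d + 14 ≤ 31 gives 11 ≤ d ≤ 17.
- Synopsis and 5.1.1: d + 28 ≤ 31 gives d ≤ 3.

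**D60.** Table 10 gives day 60 ± 3, that is 57 to 63. Counted from discharge, it is day 5 + 60 = 65 for d = 5 and 14 + 60 = 74 for d = 14. It meets the window only for d ≤ 3. Section 12.10 expects about 60 days per participant in all, which fits Table 10.

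**D21.** Last dose + 7 is day 12 for a last dose on day 5, and day 21 for a last dose on day 14. Table 10 gives day 21 ± 3 in both cases.

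**Between arms.** Under 7.3, the arms' mean D28 dates differ by exactly the difference in mean discharge day. The protocol gives no discharge forecast, so the following pairs are assumptions:

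| Assumed discharge day (drug vs placebo) | D28 visit under 7.3 | Gap |
|---|---|---|
| 7 vs 9 | 21 vs 23 | 2 days |
| 4.5 vs 11.3 | 18.5 vs 25.3 | 6.8 days |
| 5 vs 14 | 19 vs 28 | 9 days |

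The middle pair borrows the pilot trial's time to a negative test (section 2.5: 11.3 days in controls, 11.3 − 6.8 = 4.5 on the drug) as if discharge fell on that day. With start of treatment as the single origin, the gap is zero whatever the discharge day.

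**The case against.** The strongest reply is that visit timing does not define the endpoint window. Endpoints are stated until D28, Table 10 defines D1 as the first day of administration, and section 8.7 records AE onset dates, so an analyst can cut events at study day 28. Deaths can be dated at the D60 contact or, for people lost to follow-up, from medical and public records (section 9.5). This largely stands for mortality and for dated AEs, provided participation does not end at discharge. It does not help measurements that exist only on the day they are taken: symptom scores, CT, laboratory values and RT-PCR. Nor does it help AEs that nobody asks about.

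Second, only three origins differ materially, since last dose and end of treatment nearly coincide, and section 9.1 can be read as naming study days that happen to follow treatment. Both points are fair. Start of treatment, end of treatment and discharge still conflict, and nothing says which prevails.

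Third, post-discharge AEs are not ignored. Section 8.4 has participants report them, section 7.2 accepts spontaneous reports, and the D28 and D60 visits have symptom monitoring. The Visit 19 list in 7.3 also omits the blood and swab sampling that 5.1.1 and Table 10 require at D28, so it is not exhaustive. Table 10's AE row is too damaged in the available text to settle the matter. The gap is therefore a mismatch between 7.3 and 8.7, softened by self-report, and not proof that AE collection stops.

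Fourth, discharge as termination is one synopsis line against several sections. It is a contradiction to reconcile, not an operative rule.

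Fifth, two negative tests are only one of the discharge criteria, and medical evaluation is needed too (section 9.1). The link between drug effect and discharge day is plausible but not fixed.

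**Conclusion.** The follow-up schedule is wrong as written because its sections cannot all be followed. For a D5 discharge the D28 visit falls on study day 19, 28 or 33, and the 7.3 rule meets Table 10's window only for discharge on days 11 to 17. Data gathered at D28 could therefore come from study days that depend on a post-randomisation outcome which the treatment may change. The size between arms is unknown: under 7.3 it equals the difference in discharge day, 2 to 9 days across the assumed pairs above.

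A reader might go further and infer that mortality and AE rates are counted over a shorter time in the arm discharged sooner, and put a percentage on the resulting false safety advantage. The documents do not support that. No section says that events are counted to the visit date, deaths and dated AEs can largely be cut at day 28, and the protocol supplies neither discharge times nor a daily AE rate from which to compute such a figure. A reader might also infer that a D21 comparison among inpatients is planned. The protocol restricts the procedures and names the D21 period, but does not specify that comparison.

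The D15 primary efficacy endpoint and the sample size are unaffected.

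**What to change.** - Use one origin for every visit and endpoint window. Start of treatment, as in Table 10, is already there. Align the synopsis and sections 5.1.1, 7, 7.3 and 9.1 with it, including D21 and D60.
- Reconcile synopsis item 6 with sections 9.1 and 9.3, so that discharge does not end study participation. This concerns data collection only, not when anyone is discharged.
- List AE questioning at Visits 19 and 20 in section 7.3 for all participants, to match section 8.7.
- State that between-arm comparisons at D21 are limited to outcomes known for everyone, such as vital status, still in hospital or not, and ventilation. Do not compare laboratory or viral-load values among inpatients only.

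The cost is protocol wording and one AE question at visits already planned. The number of participants does not change.

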2.3. PRE-CLINICAL STUDIES

In vitro studies, conducted in China, demonstrated good activity and selectivity of AZVUDINE on cells infected with SARS-CoV-2. An *in vitro* activity study demonstrated that the active metabolite CL-236 of AZVUDINE has an antiviral activity against coronavirus. The EC50 is 1.51 μ M and the selectivity index is 60 (Table 2: CL-236 (active metabolite of AZVUDINE) inhibits coronavirus activity). The test results support speculation of the mechanism of action of AZVUDINE against COVID-19.

Compound	EC ₅₀ (μM)	CC ₅₀ (μM)	SI
CL-236	1,51	89.94	60
Compound	EC ₅₀ (μM)	CC ₅₀ (μM)	SI
Ribavirin	17,9	>409	>23

Table 2: CL-236 (active metabolite of AZVUDINE) inhibits coronavirus activity

Another AZVUDINE *in vitro* test showed that the active metabolite of AZVUDINE, CL-236, has good antiviral activity against COVID-19 and its EC50 against SARS-CoV-2 is about $3.2\,\mu\text{M}$, which is equivalent to Remdesivir, the positive control drug.

[figure not shown]

Figure 2: Graph showing the EC50 of CL-236

In vivo studies have demonstrated the safety of AZVUDINE. Administration of AZVUDINE in single doses of 0.24 mg/Kg, 0.48 mg/Kg or 0.96 mg/Kg had no significant effect on the circulation and respiratory system of Beagle dogs. The results of the *in vivo* toxicity test in Beagle dogs receiving AZVUDINE for 39 weeks showed that at high doses of 0.3 mg/kg, the main target organs are the gastrointestinal tract and the hematopoietic immune system. After 4 weeks of drug withdrawal, the toxic reaction can be basically restored. No toxicity reaction was observed in the 0.03 and 0.1 mg/kg dose groups. Systemic exposure to the drug has shown that the level of observable adverse events

(NOAEL) is equivalent to 20-30 times the human exposure at the maximum clinical dose used in phase II (4 mg).

Dosages of 1.2 and 2.4 mg/Kg were safe for the nervous system of mice and the dose of 4.8 mg/Kg reduced the sleep time of mice induced by pentobarbital sodium threshold. Sodium pentobarbital is a central depressant with sedative and hypnotic effects. When sodium pentobarbital is administered in threshold doses, drugs that could stimulate or inhibit the central nervous system can increase or decrease the sleep time of mice.

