For Early Termination (ETA) of treatment, participants should follow the routine for visit 17: End of Treatment (D15), in advance. Discharge from the hospital may be

granted before the end of the 14-day treatment period if clinically indicated and the treatment has been completed.

The period between randomization and the end of treatment will be up to 14 days and there may be early termination (AT) or worsening. Participants who, even after the end of treatment, still remain in the hospital, will undergo the procedures and tests for safety and efficacy monitoring on D21 and follow the follow-up schedule from D28 to D60.

During the follow-up period, the participant will be required to return within 28 and 60 days of hospital discharge for follow-up visits.

The first day of treatment will be day 1 and will last up to 14 days.

Treatment will be terminated early when two consecutive RT-PCR tests are negative (criteria for hospital discharge) and may be stopped early in the event of participant dropout, or in the event of EAG.

All participants will undergo efficacy and safety evaluations. Blood samples and respiratory samples (oropharyngeal and nasopharyngeal swabs) will be obtained on days D1, D3, D5, D7, D9, D11, D13, and D14 (while hospitalized); and day D21 (participants still hospitalized after completion of treatment) and days D28 and D60 (upon return to the center or if still hospitalized). Detailed information about the visit is in section 7.3.

After discharge from the hospital, research participants should follow the instructions below in accordance with the care and attention specified by the research center:

- Stay in recovery for 3 to 6 weeks;
- Use face masks when necessary;
- Sanitize your hands and do not share personal objects;
- Avoid contact with people in the risk group, especially;

• Inform the Principal Investigator, or his/her team, immediately in case of fever and/or respiratory symptoms.

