- Time to normalization of respiratory rate to levels ≤ 24rpm, in room air; [Period: until D15, D21 and D28, approximately 14-30 days]
- Frequency of supplemental oxygenation or non-invasive ventilation; [Period: until D15, D21 and D28, approximately 14-30 days].
- Frequency of invasive mechanical ventilation or extracorporeal membrane oxygenation (ECMO); [Period: until D15, D21, and D28, approximately 14-30 days].
- Proportion of moderate cases that progressed to severe cases requiring intensive care unit (ICU) care; [Period: until D15, D21, and D28, approximately 14-30 days].
- Length of hospital stay; [Period: until D15, D21 and D28, approximately 14-30 days].
- Occurrence of drug interactions; [Period: until D15, D21 and D28, approximately 14-30 days].
- Frequency and intensity of adverse events; [Period: until D15, D21 and D28, approximately 14-30 days].
- Frequency and intensity of unexpected adverse events; [Period: until D15, D21 and D28, approximately 14-30 days].
- Frequency and intensity of serious adverse events; [Period: until D15, D21 and D28, approximately 14-30 days].
- Taxa de mortalidade por todas as causas durante o estudo; [Período: até o D15, D21
 e D28, aproximadamente 14-30 dias]
- Evaluate the tolerability of AZVUDINE (FNC) use at 5mg/day regimen for up to 14 days: [Period: until D15, approximately 14 days].
 - Calculating treatment adherence;

- Total time of use of AZVUDINE (FNC);
- o Proportion of participants who withdrew consent;
- o Proportion of participants who dropped out of treatment.

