VISIT 3-16: PROCEDURE (D1-D14)

The treatment period will start on D1 according to randomization.

The treatment will last up to 14 days, and may be stopped early in case of treatment success (2 consecutive negative RT-PCR tests), participant dropout, or at the Principal Investigator's option, if deemed necessary for the safety of the participant.

For the **Early Termination (ETA)** of treatment, participants should follow the routine from visit 17: End of Treatment (D15), in advance.

The Principal Investigator for the study will be available to answer any questions.

The experimental drug should be administered daily at 8 pm to minimize the risk of falling, since in preliminary studies, it was observed that vertigo (incidence ≥5%) appears to be an AE likely related to FNC. However, no restrictions on meals.

The following procedures will be performed in the V3-16 visits:

- Administration AZVUDINE or PLACEBO daily, at the same time at 8pm, to minimize the risk of falling, since in preliminary studies, it was observed that vertigo (incidence ≥5%) may be an AE likely related to FNC;
- Monitoring drug interactions and AEs on a daily basis;
- Monitoring symptoms, vital signs, oximetry and blood glucose daily;
- Collection of blood samples and respiratory sample (nasal and oropharyngeal swab) for safety and efficacy monitoring tests every 48h);
- CT scan of the lung every 4 days and electrocardiogram on days D1 and D11;

The Principal Investigator may adjust the procedures performed during treatment according to the condition of the research participant and the results of clinical examinations.

VISIT 17: END OF TREATMENT (D15)

At the end of treatment or discontinuation of the investigational drug or PLACEBO, all participants will be required to undergo procedures and tests for safety and efficacy monitoring. The procedures should be performed before discharge from the hospital approximately 24 hours after the administration of the last dose of the investigational drug or PLACEBO, because for the 5 mg dose of AZVUDINE, the mean half- life is 13.8 hours, and it is excreted in the urine within 24 hours.

The treatment will last up to 14 days, and may be stopped early in case of

treatment success (2 consecutive negative RT-PCR tests), participant dropout, or at the Principal Investigator's option, if deemed necessary for the safety of the participant.

The following procedures will be performed at the V17 visit:

- Monitoring drug interactions and AEs;

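### The D28 and D60 visit lists omit adverse event collection and safety bloods, and Table 10 footnote 3 makes tests there conditional, contradicting sections 5.1.1, 7.1.2 and 8.7

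*Protocol*

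**What the plan says.** Section 7.3 gives each visit its own list of procedures. AE monitoring and blood sampling are on the lists for V3-16, V17 (D15) and V18 (D21). Footnote 5 to Table 10 restricts V18 to participants still in hospital.

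For D28 the list begins "The following procedures will be performed at the V19 visit" and contains symptoms, vital signs, oximetry, glucose, lung CT and ECG. For D60 it contains symptoms, vital signs, oximetry, glucose and a pregnancy test, followed by "The Principal Investigator may order tests according to the participants' previous results". Footnote 3 to Table 10 says that procedures and examinations planned "at visit D28 and D60 will be determined by the Principal Investigator according to the participants' previous examinations".

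Other sections say something different:
- Section 5.1.1 states that blood and respiratory samples will be obtained on "days D28 and D60 (upon return to the center or if still hospitalized").
- Section 7.1.2 names D28 and D60 among the fixed laboratory days for the liver, kidney, inflammatory and immunological endpoint. That endpoint and the AE and SAE endpoints run to D28, for example "Frequency and intensity of serious adverse events; [Period: until D15, D21 and D28, approximately 14-30 days".
- Section 8.7 makes the investigator responsible for recording all events "during the study period from the first dose to the end of follow-up, regardless of severity and causal relationship to the study drug".
- Section 11.3 makes SAE occurrence the dependent variable of the logistic model for the safety part of the primary objective.

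**The concern.** The endpoint definitions and section 8.7 promise safety data to D28 and to the end of follow-up. The visit lists, which site staff work from and from which data forms are usually built, do not collect them. A statistical analysis plan cannot repair this, because the data would not exist.

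Two consequences matter for the comparison between arms. First, AE collection is daily in hospital and unscheduled afterwards, so the number of events recorded depends on when a participant goes home. Second, if D28 bloods are drawn only where earlier results prompt them, D28 laboratory values are missing by a rule tied to post-randomisation results. Symptom checks cannot fill that gap: the events of special interest in section 8.3 include AST or ALT above reference and eGFR below 30 mL/min, which only a blood test shows.

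**Working it through.** The plan states no figure to reproduce, so the check is a side-by-side reading.

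| Place in Protocol | AEs at D28 | AEs at D60 | Safety bloods at D28 | Safety bloods at D60 |
|---|---|---|---|---|
| 5.1.1 | no visit item given | no visit item given | fixed | fixed |
| 7.1.2 | endpoint window reaches D28 | beyond the window | fixed laboratory day | fixed laboratory day |
| 7.3, V19 and V20 lists | not listed | not listed | not listed | not listed; investigator may order |
| Table 10 rows | appears blank | appears blank | marked | appears blank |
| Table 10 footnote 3 | investigator decides | investigator decides | investigator decides | investigator decides |
| 8.7 | required | required | not addressed | not addressed |

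The Table 10 entries come from lining up a table that is broken in the available text, so they are inferences. The section 7.3 lists carry the point without them. The mark for footnote 3 sits on the D60 column heading, but its wording names D28 as well.

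**Step 1: last scheduled AE query.** V18 is for inpatients only, and V19 and V20 list no AE item. For a participant who has gone home, V17 is therefore the last visit that lists one.

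**Step 2: what remains after V17.** There are the general duties in sections 7.2 and 8.7, symptom monitoring at V19 and V20, and section 8.4, which asks participants whose events develop after discharge to contact the team.

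**Step 3: why the arms could differ.** Two consecutive negative RT-PCR tests end treatment and are a discharge criterion (synopsis and 5.1.1). Section 2.6.3 expects azvudine to bring negativity sooner. If it does, azvudine participants may leave hospital earlier and have fewer days under daily AE monitoring, which would lower their recorded AE count without their being safer. In the other direction, section 2.5 reports ALT and AST rises as the main reactions in Hope 4. If azvudine raises them here, footnote 3 would send more azvudine than placebo participants for D28 tests. The two effects push opposite ways, so the net direction cannot be predicted.

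**Step 4: when V19 and V20 fall.** Section 7.3 places V19 two weeks, and V20 60 days, after discharge. Table 10 counts D28 and D60 from the start of treatment. Section 5.1.1 refers to 28 and 60 days from discharge. As an illustration with assumed discharge days:
- Discharge on D15: 7.3 puts V19 at D15 + 14 = D29, within the ±3-day window around D28.
- Discharge on D6: 7.3 puts V19 at D6 + 14 = D20, which is 8 days before D28 and outside that window. Counting 28 days from discharge gives D34.

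So for early discharges, even an AE query at V19 might not reach the end of the D28 window unless the timing is settled.

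**The case against.** The strongest reply is that the protocol does not abandon safety collection after discharge. Section 8.7 keeps a duty to monitor and record throughout, section 7.2 provides for asking participants about events without prompting, and section 7.3 describes V19 and V20 as visits to monitor safety and efficacy. This stands: AE capture after V17 is unscheduled, not absent. It does not remove the inconsistency, because no follow-up visit list puts those duties into practice.

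A reader might infer that D28 bloods are simply left to the investigator. The document does not support that. Section 5.1.1, the endpoint text and, as far as it can be read, Table 10 all fix them; only footnote 3 and the silence of the V19 list point the other way. Selective missingness follows only if footnote 3 is the text that sites follow.

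A reader might also count the days from V17 to D28 (28 − 15 = 13 after a full course) as lost data. They are an interval between queries, and a query at D28 could look back over them.

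Two pharmacological arguments are also tempting. Section 7.3 says of V17 that "The procedures should be performed before discharge from the hospital approximately 24 hours after the administration of the last dose", and the stated 13.8-hour half-life implies that some drug is still present then. That does not make V17 a wrong end-of-treatment visit, and it has no bearing on what V19 and V20 omit. Section 2.3 says of the dog study that "After 4 weeks of drug withdrawal, the toxic reaction can be basically restored". That followed the high dose given for 39 weeks, with no toxicity at the two lower doses, and the text does not say that four weeks were needed. It is weak evidence for delayed toxicity after at most 14 days.

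**Conclusion.** The point holds as a contradiction within the protocol that affects safety ascertainment. The section 7.3 lists for D28 and D60, together with footnote 3, cannot be squared with sections 5.1.1, 7.1.2 and 8.7. For D28 bloods they also conflict with the marks in Table 10.

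Its reach is the AE and SAE endpoints, the D28 laboratory endpoint and the primary safety model. The primary efficacy endpoint ends at D15 and is untouched. The size of any bias cannot be computed, because the document gives neither event rates after discharge nor expected discharge times by arm. The conclusion that ascertainment could differ by arm assumes that sites follow the visit lists and footnote 3, and that treatment affects discharge timing or earlier laboratory results. The protocol itself anticipates both kinds of effect.

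**What to change.** - Reconcile sections 5.1.1, 7.1.2, 7.3 and 8.7 and Table 10 with its footnote 3.
- Add collection of AEs and SAEs since the last visit to V19 and V20, in section 7.3 and in the AE row of Table 10.
- Make the D28 safety bloods (blood count, liver and kidney function) unconditional for all participants, as 5.1.1, the endpoint text and Table 10 already indicate. List them under V19 and remove D28 from footnote 3.
- For D60, either schedule the laboratory tests in Table 10 and the V20 list, or delete D60 from the laboratory days in 5.1.1 and the endpoint text (also in the synopsis, section 4 and the section 11.3 table).
- State one reference point for the timing of V19 and V20 and use it throughout, so that the D28 window is covered whatever the discharge day.

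No change to concomitant medication is needed for this point; section 6.6 plans that collection for visits 1 to 17.

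The cost is protocol and eCRF wording, a few AE questions at two existing visits, and routine bloods at a D28 visit where Table 10 appears to mark them already.
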